National Institutes of Health (NIH)-funded investigators and clinical trial site staff who are responsible for the conduct, management, or oversight of NIH-funded clinical trials have completed Human Subjects Protection and ICH GCP Training.

[figure not shown]
The protocol, informed consent form(s), recruitment materials, and all participant materials will be submitted to the Institutional Review Board (IRB) for review and approval. Approval of both the protocol and the consent form must be obtained before any participant is enrolled. Any amendment to the protocol will require review and approval by the IRB before the changes are implemented to the study. In addition, all changes to the consent form will be IRB-approved; a determination will be made regarding whether a new consent needs to be obtained from participants who provided consent, using a previously approved consent form.

1 PROTOCOL SUMMARY

1.1 Synopsis

Title:	Pharmacokinetics and Safety of Caffeine in Neonates with Hypoxic-Ischemic Encephalopathy
Study Description:	This is a phase I, open-label, dose-escalating pharmacokinetics (PK) and safety study of caffeine in neonates with hypoxic-ischemic encephalopathy undergoing therapeutic hypothermia. We hypothesize that drug clearance will be $\geq 20\%$ lower than expected for gestational age and birth weight and that the incidence of adverse events will be within 20% of published results of neonates treated with therapeutic hypothermia in the NICHD Total Body Hypothermia for Neonatal Encephalopathy trial.
Objectives:	
Primary Objective: Characterize the PK of caffeine in neonates undergoing therapeutic hypothermia for hypoxic-ischemic encephalopathy (HIE).
 
Secondary Objectives: Characterize the safety of caffeine in neonates undergoing therapeutic hypothermia for HIE. Evaluate the preliminary effectiveness of caffeine in reducing brain injury in neonates with HIE.

Endpoints:	
Primary Endpoint: PK: Caffeine clearance
 
Secondary Endpoints: Safety: Adverse events Note: Seizures and necrotizing enterocolitis will be AEs of special interest Preliminary effectiveness: Death, abnormal MRI findings, neurodevelopment at 18-24 months

Study Population:	
Inclusion Criteria
 
 1. Documented informed consent from parent or guardian 2. ≥ 36 weeks gestational age at birth 3. Receiving therapeutic hypothermia for a diagnosis of HIE 4. Intravenous (IV) access 5. Postnatal age < 24 hours 
Exclusion Criteria
 
 1. Receiving > 1 anti-epileptic drug for seizures 2. Sustained (>4 hours) heart rate > 180 beats per minute 3. Known major congenital anomaly 4. Any condition which would make the participant, in the opinion of the investigator, unsuitable for the study
Phase:	1
Description of Sites/Facilities Enrolling Participants:	Up to 3 US Neonatal Intensive Care Units, including The University of North Carolina at Chapel Hill Newborn Critical Care Center
Description of Study Intervention:	
Cohort 1 (N = 9): Caffeine IV 20 mg/kg loading dose, followed by 5 mg/kg q 24 hours x 2 doses.
 
Cohort 2 (N = 9): Caffeine IV 20 mg/kg loading dose, followed by 10 mg/kg q 24 hours x 2 doses.
 
Note: An interim safety analysis will be conducted following the follow-up period in the final cohort 1 participant and prior to enrolling in cohort 2.

Study Duration:	24 months
Participant Duration:	24 months

1.2 Schema

1.3 Schedule of Activities (SoA)

	Screen/ Baseline	Treatment	Follow-up Period	Discharge/Transfer /Death	Final study assessment
Time point	< 24 hours postnatal age	Study day 1-3	7 days following last caffeine dose		18-24 Months
Informed consent	X				
Demographics	X				
Neurological Exam	X			X	X
Weight	X	X	X	X	X
Medical history	X				X ¹
Respiratory Support	X ²	X ²	X ²	X	
Laboratory evaluations ³	X	X	X		
Urine output	X	X	X		
Caffeine administration ⁴		X			
Concomitant medications		X	X		
Adverse events ⁵		X	X		
PK sampling ⁶		X	X		
Epigenetic sampling ⁷		X	X		
Clinical events of interest ⁸		X	X		
Head imaging ⁹		X	X	X	
Hearing screen				X	
Surgical procedures		X	X	X	
Bayley-III composite scores and GMFCS					X

¹ Follow-up visit will include information on hearing impairment requiring hearing aids, blindness, and cerebral palsy diagnosis. ² Highest respiratory support (room air, oxyhood, nasal cannula/CPAP, or mechanical ventilation) and maximum FIO₂ exposure during each 24-hour period. ³ See Section 8.2.1. ⁴ Includes exact start, stop, and flush times for all caffeine doses. ⁵ Seizures requiring > 1 anti-epileptic drug and necrotizing enterocolitis are adverse events of special interest. ⁶ Date and time for each sample. ⁷ Obtained from scavenged blood samples, if available. ⁸ Includes death, sepsis, disseminated intravascular coagulopathy, hypotension, hypertension, hepatic dysfunction, acute kidney injury, persistent pulmonary hypertension, and thrombocytopenia. ⁹ Includes cranial ultrasounds and head CT, if done per standard of care, and brain MRI.

2 INTRODUCTION

2.1 Study Rationale

Hypoxic-ischemic encephalopathy (HIE) due to perinatal asphyxia is a common and often fatal disease in neonates. HIE occurs in nearly 1% of live births.¹ Neonates with HIE experience a temporary interruption in blood flow to the brain and body around the time of delivery. This results in tissue hypoxia with subsequent damage to the brain and other vital organs.² Encephalopathy manifests as abnormalities in the neurological exam, which can include seizures and alterations in levels of consciousness, muscle tone, and breathing patterns. The severity of encephalopathy is categorized into three stages (mild, moderate, and severe) based on the Sarnat grading scale.³

Therapeutic hypothermia reduces morbidity and mortality in neonates with HIE. Therapeutic hypothermia reduces the risk of death or neurodevelopmental impairment (NDI) at 18-24 months in neonates with moderate to severe HIE (number needed to treat is 7).⁴⁻¹⁰ Even with therapeutic hypothermia, mortality or NDI remains ~60% in neonates with HIE.¹⁰ As a result, there is an **urgent, unmet public health need** to develop adjuvant therapies to improve neurodevelopmental outcomes in this population.

Adjuvant therapies are being investigated to improve outcomes in neonates with HIE (Table 1). These agents primarily target the effects of reperfusion injury in the brain which occurs 6-48 hours following the initial insult as a result of inflammation, oxidative stress, and excitotoxicity leading to cell death.¹¹ All studies, with the exception of erythropoietin and allopurinol, are early phase trials and none of these therapies are currently approved or have demonstrated definitive benefits for HIE. Caffeine has not yet been investigated for neuroprotection in neonates with HIE.

Table 1. Adjuvant therapies under investigation for HIE

Therapy	Clinicaltrials.gov
Erythropoietin ^{12,13}	NCT01913340; NCT02811263*
Darbepoetin alfa ^{14,15}	NCT01471015
Autologous cord blood stem cells ^{16,17}	NCT02612155; NCT02434965
Melatonin ¹⁸	NCT02621944
Xenon ^{19,20}	NCT00934700; NCT01545271
Allopurinol ^{21,22}	NCT03162653**
Topiramate ²³	NCT01241019; NCT01765218
Clonidine	NCT01862250

Anticipated Phase III completion: *September 2022; **December 2020

2.2 Background

Caffeine is an appealing therapeutic for neuroprotection in neonates with HIE. Caffeine given for apnea of prematurity reduces NDI at 18-21 months.^{24,25} In addition, methylxanthines (the same drug class as caffeine) also reduce the incidence of acute kidney injury in neonates with HIE.²⁶⁻³² Caffeine competitively binds to and blocks the action of adenosine receptors in the brain. Mechanisms by which caffeine may offer neuroprotection are the reversal of hypoxia-induced delayed maturation of oligodendrocytes, the cells which produce myelin in the central nervous system,³³ and anti-inflammatory and anti-oxidative properties which protect against reperfusion injury.³⁴⁻³⁶ Methylxanthines reduce neuronal cell death in animal models of HIE.³⁷⁻³⁹ Thus, caffeine may improve neurologic outcomes in neonates with HIE.

The pharmacokinetics (PK) and safety of caffeine in neonates with HIE is unknown. Caffeine PK and safety are well-described in neonates treated for apnea of prematurity.⁴⁰⁻⁴² However, ischemic injury and therapeutic hypothermia alter the PK of medications, including morphine and gentamicin.^{43,44} As caffeine is primarily metabolized by the hepatic cytochrome enzyme CYP1A2 and excreted in the urine, ischemic injury to the liver and kidneys may reduce its clearance. Additional areas of uncertainty regarding caffeine in the setting of HIE include optimal dosing and safety. There is evidence that caffeine at doses > 36 mg/kg may lower seizure threshold.⁴⁵⁻⁴⁷ Therefore, PK and safety data for caffeine in the setting of HIE and therapeutic hypothermia are needed.

Brain injury on MRI is a reliable biomarker for neurodevelopmental outcome in neonates with HIE. The NICHD Neonatal Research Network validated an MRI scoring system that categorizes severity of brain injury in the therapeutic hypothermia trial.⁵ Abnormal MRI findings were lower in the treatment group compared to the control group (48% vs 65%) and the results were independently associated with NDI at 18-22 months⁴⁸ and intelligence quotient at 6-7 years of age.⁴⁹

In-hospital morbidities in a cohort of neonates receiving caffeine while undergoing therapeutic hypothermia for HIE are similar to those published in cooling trials. We reviewed data from the Pediatric Medical Group, a national consortium of neonatal intensive care units (NICUs) with ~90,000 admissions per year.⁵⁰ We examined all inborn neonates with HIE who received therapeutic hypothermia and methylxanthine therapy (caffeine or aminophylline) in the first three postnatal days between 2007-2016. We recorded frequencies of death, mechanical ventilation, acute kidney injury (AKI; defined as creatinine rise > 0.3 mg/dL in a 48-hour period), hepatic dysfunction, receipt of anticonvulsant medication (defined as phenobarbital, fosphenytoin, or levetiracetam), and duration of hospitalization. We compared these frequencies to the results from three trials of therapeutic hypothermia.⁴⁻⁶ There were 26 neonates who received methylxanthines in the setting of therapeutic hypothermia – 17 received caffeine, 8 received aminophylline, and one neonate received both. The frequency of AKI in neonates receiving caffeine was 25% (3/12) (Table 2).

Table 2. Mortality and morbidity in neonates with HIE who received methylxanthines and in treated (i.e., received therapeutic hypothermia) groups from therapeutic hypothermia trials.

	Caffeine group (n=18)	Aminophylline group (n=9)	Treated* Groups in Previous Trials (n=373)
Death	13 (2/16)	0 (0/6)	19-33 ⁴⁻⁶
Duration of hospitalization in days, median (IQR)	19 (16-32)	15 (9-16)	20 ⁵
Renal			
Creatinine rise > 0.3 mg/dL in 48 hour period	25 (3/12)	56 (5/9)	N/A
Creatinine > 1.0 mg/dL	38 (5/13)	89 (8/9)	65 ⁴
Hepatic			
Prothrombin Time > 16 s AST > 200 U/L or ALT >100 U/L	100 (7/7) 56 (5/9)	86 (6/7) 38 (3/8)	41 ⁶ 20-38 ^{4,5}
Neurologic			
Receiving anticonvulsant in first postnatal week	44 (8/18)	44 (4/9)	38 ⁵

*Treated indicates infants enrolled in the trials who received therapeutic hypothermia. Column percentages unless otherwise noted. IQR: Interquartile Range; AST: Aspartate Aminotransferase; ALT: Alanine Aminotransferase.

Determining the PK and safety of caffeine in neonates undergoing therapeutic hypothermia for HIE is an urgent, unmet public health need. Investigating caffeine as an adjuvant therapy for therapeutic hypothermia represents an ideal opportunity to approach the problem of the research gap of drugs in neonates with HIE because: 1) HIE is a relatively common diagnosis in the perinatal period; 2) Neonates with HIE are at increased risk of death or neurodevelopmental impairment; and 3) Preventing mortality and morbidities associated with HIE has life-long benefits. This study will provide the necessary first step to design next phase trial to evaluate the preliminary effectiveness of caffeine in reducing brain injury in neonates with HIE. If successful, caffeine will offer providers a cost-effective and safe treatment for neuroprotection in neonates with HIE.

2.3 Risk/Benefit Assessment

2.3.1 Known Potential Risks

Risks of Blood Drawing

There are small risks to blood sampling, usually some pain/discomfort with the blood stick and blood loss. Every effort will be made to avoid additional (to standard of care) sticks for this study and will time clinical blood draws to coincide with timed samples, using existing intravenous lines when possible. A maximum of 7 plasma PK samples per participant will be collected during the treatment and follow-up periods. PK blood samples will be obtained only if laboratory tests are being collected per routine medical care. Each sample will be limited to a volume of 250 μ L. The expected total maximum amount will be no more than 1.75 mL (about 1/3 of a teaspoon).

Caffeine⁵¹

1. Published literature reports have raised questions regarding possible association between the use of methylxanthines, such as caffeine, and the development of necrotizing enterocolitis (NEC) in premature neonates, although a causal relationship has not been established.^{52,53}
2. Caffeine is a central nervous system stimulant and in cases of caffeine overdose, seizures have been reported.⁵⁴
3. Caffeine increases heart rate and should be used with caution in neonates with cardiovascular disease.
4. Caffeine should be used with caution in neonates with impaired renal or hepatic function.

2.3.2 Known Potential Benefits

Clinical studies in neonates have demonstrated that caffeine reduces NDI at 18-21 months in premature neonates treated for apnea of prematurity.^{24,25} Preclinical studies in rats have found that caffeine offers neuroprotection following perinatal hypoxic-ischemic injury.^{34,38,39} Therefore, a reduction in brain injury and NDI are potential benefits for participants enrolled in the study. Conclusions drawn from this study will benefit neonates receiving caffeine in the setting of therapeutic hypothermia for HIE in the future through better understanding of dose response and characterization of the safety profile of caffeine.

2.3.3 Assessment of Potential Risks and Benefits

Given the high incidence of mortality and NDI in neonates with HIE, we propose that the value of the information to be gained in this study outweigh the potential risks of exposure to caffeine. We have minimized these potential risks by using a dose of caffeine that is equivalent to the dose ranges used on-label for apnea of prematurity in preterm neonates. We will exclude neonates with difficult to control seizures (i.e., receiving > 1 anti-epileptic drug [AED]), tachycardia (defined as heart rate > 180 beats per minute for > 4 hour), or major congenital anomalies, including congenital heart disease. We will collect data on seizures and necrotizing enterocolitis as safety events of interest. We will review safety data prior to dose escalation between cohorts.

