5.2 Exclusion Criteria

1. Receiving $>$ 1 anti-epileptic drug for seizures
2. Sustained (>4 hours) heart rate $>$ 180 beats per minute
3. Known major congenital anomaly
4. Any condition which would make the participant, in the opinion of the investigator, unsuitable for the study

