8.3.8 Events of Special Interest

1. Seizures will be defined by the receipt of > 1 AED, as we are interested in identifying seizures which are difficult to control.
2. Necrotizing Enterocolitis - Bell Stage II or III⁵⁷

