9.2 Sample Size Determination

- **Pharmacokinetics**

A sample size of 9 neonates in each dosing cohort will be powered ($\geq 80\%$) to target a 95% confidence interval within 60% and 140% of the geometric mean estimate of clearance (assuming 36% between subject variability in clearance, which is based on existing literature of caffeine PK in neonates).⁵⁸⁻⁶⁰

- **Safety**

The frequency of seizures in the treated group of the NICHD trial was $\sim 40\%$.⁵ Estimation of the probability of seizures in our study will be based on the combined sample of 18 patients. For comparison with historical data, the null hypothesis that the frequency of seizures is 40% will be rejected if 11 or more adverse events (in 18 patients) are observed. The event probability will be no wider than 21% on each side of the point estimate and this will provide a power of 86%. The alternative hypothesis is that the frequency of seizures is $> 61\%$ or $< 19\%$ in our study (i.e., $> 21\%$ on either side of the point estimate of 40%).

- **Preliminary effectiveness**

This is an exploratory aim and will not be sufficiently powered to detect a significant reduction in brain injury on MRI. However, we estimate that there will be a trend toward risk reduction of brain injury in enrolled neonates compared to treated neonates in the NICHD trial.

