9.4.3 Analysis of the Secondary Endpoint(s)

- **Preliminary Effectiveness**

We will use MRI brain images from enrolled neonates to assess the severity of brain injury according to the scoring strategy used in the NICHD trial: 0 (normal MRI), 1A (minimal cerebral lesions), 1B (extensive cerebral lesions), 2A (basal ganglia thalamic injury), 2B (2A with cerebral lesions), and 3 (hemispheric devastation). We will dichotomize these results into normal and abnormal and use logistic regression to compare neonates in cohorts 1 and 2 to treated neonates in the NICHD trial to calculate a risk ratio for abnormal MRI with 95% confidence

intervals, adjusting for potential confounders such as severity of encephalopathy and presence of seizures.

We will use the composite cognitive, language, and motor scores on the Bayley-III at the 18-24 month follow-up visit to assess NDI. We will define NDI as any of the following: composite cognitive, language, or motor score < 85, hearing impairment requiring hearing aids, a diagnosis of blindness, or GMFCS level ≥ 3 . We will use logistic regression to compare neonates in cohorts 1 and 2 to treated neonates in the NICHD trial to calculate a risk ratio for NDI with 95% confidence intervals.

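### Infants on more than one AED are excluded at entry, but the plan sets no matching restriction on the NICHD treated arm used as comparator for seizures, MRI and NDI

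*Combined protocol and SAP*

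**What the plan says.** Exclusion criterion 1 in Section 5.2 (repeated in the synopsis) is "Receiving $>$ 1 anti-epileptic drug for seizures". Section 2.3.3 gives the reason: "We will exclude neonates with difficult to control seizures (i.e., receiving > 1 anti-epileptic drug [AED". Infants may be enrolled and given the first dose up to 24 hours of age (Sections 5.1, 5.5 and 8.1.2).

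The seizure outcome uses the same threshold. Section 8.3.8, repeated in 9.4.4.1, says: "Seizures will be defined by the receipt of > 1 AED, as we are interested in identifying seizures which are difficult to control".

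Three results are compared with the NICHD treated arm:

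- **Seizures** (Section 9.2), against a fixed rate: "the null hypothesis that the frequency of seizures is 40% will be rejected if 11 or more adverse events (in 18 patients) are observed".
- **Abnormal MRI** (Section 9.4.3), by logistic regression "adjusting for potential confounders such as severity of encephalopathy and presence of seizures". Section 9.1 calls a risk ratio of 0.7 to 1.1 favourable.
- **NDI** (Section 9.4.3): "We will use logistic regression to compare neonates in cohorts 1 and 2 to treated neonates in the NICHD trial". No covariate is named for this model.

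No section restricts, matches or re-weights the NICHD arm to infants on at most one AED.

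**The concern.** The exclusion removes infants whose seizures were already hard to control. Such infants would be expected to have more brain injury and more impairment, and on the plan's own definition they already have the seizure outcome. If the comparator keeps them, it starts from a worse position than the enrolled infants, and a difference would appear with no caffeine effect.

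The MRI adjustment has a second weakness. Its seizure covariate is not fixed as a pre-dose variable. Seizures after dosing are an event of special interest in this trial, so the model as worded may adjust for a possible effect of the drug.

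Section 4.2 says this study is to inform a larger trial. The main risk is that a harm signal on seizures is muted. A flattering MRI or NDI ratio carried into that design is the other risk.

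**Working it through.** **Inputs from the documents.** Seizure benchmark 40%, n = 18, rejection at 11 or more (Section 9.2). NICHD treated-arm abnormal MRI rate 48% (Section 2.2: "Abnormal MRI findings were lower in the treatment group compared to the control group (48% vs 65"%). Death or NDI about 60% with cooling (Section 2.1; illustration only, since it is a composite from a meta-analysis and not the NICHD NDI rate).

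**Assumptions.** p is the share of an NICHD-like population on more than one AED by enrolment; r is the event rate among those infants. The documents give neither. The range shown is p = 5% to 20%, with no drug effect.

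**The plan's own figure.** The rule of 11 or more of 18 has exact one-sided error 5.8% at a true rate of 40%. Its exact power at 61%, the upper limit in "The alternative hypothesis is that the frequency of seizures is $> 61\%$ or $< 19\%$ in our study", is 59.8%, not the stated 86%. Power of 86% is reached only near a true rate of 70%. That is a separate defect; 5.8% and 59.8% are the reference values below.

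**Abnormal MRI, crude.** Rate among those retained = (0.48 − p·r)/(1 − p). Dividing by 0.48 gives the risk ratio. At r = 0.9:

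| p | Retained rate | Risk ratio |
|---|---|---|
| 5% | (0.48 − 0.045)/0.95 = 0.458 | 0.95 |
| 10% | (0.48 − 0.09)/0.90 = 0.433 | 0.90 |
| 20% | (0.48 − 0.18)/0.80 = 0.375 | 0.78 |

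Over r = 70% to 100%, the extremes are 0.98 (p = 5%, r = 70%) and 0.73 (p = 20%, r = 100%). These are unadjusted ratios. At p = 10% and r = 90%, a true crude ratio of 1.2 would appear as 1.2 × 0.903 = 1.08, inside the range called favourable.

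**NDI, illustration.** The same formula with 0.60 and r = 0.9 gives 0.97, 0.94 and 0.88 at p = 5%, 10% and 20%. With no covariate named, nothing in the plan offsets this.

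**Seizures.** If every excluded infant is among the 40%, the retained rate is (0.40 − p)/(1 − p). The last column applies the odds ratio that takes 40% to 61%, (0.61/0.39)/(0.40/0.60) = 2.35, to the retained rate.

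| p | Expected rate, no drug effect | P(11 or more of 18), no drug effect | Power for a harm of that odds ratio |
|---|---|---|---|
| 0% | 40.0% | 5.8% | 59.8% |
| 5% | 36.8% | 3.2% | 48.6% |
| 10% | 33.3% | 1.4% | 35.8% |
| 20% | 25.0% | 0.1% | 10.9% |

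This table treats the 40% as a rate of the more-than-one-AED event. Section 9.2 does not define it that way, and Table 2 in Section 2.2 gives 38% of the NICHD arm on any anticonvulsant in the first week. Infants on more than one AED are a subset of those on any. If the 40% counts any anticonvulsant, the benchmark is too high for this outcome before selection is considered, and the error runs in the same direction.

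**The covariate.** Section 9.4.3 needs infant-level NICHD data for its adjustment, while Section 9.1 speaks of published results. In this trial, Section 8.1.1 lists concomitant medications at baseline, but the Schedule of Activities (1.3) does not mark them there and Section 6.5 covers only the period of drug administration. Section 8.1.1 has no explicit seizure item.

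**The case against.** A reader might infer that selection alone makes caffeine look protective and safe. The documents do not support that.

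- NICHD eligibility and AED use at entry are not in the documents. That the arm contains infants on more than one AED is an inference from silence.
- The size depends on p. At p = 5% the crude MRI ratio is 0.95 at r = 90%, a small shift. Section 5.5 makes infants eligible as soon as cooling is decided, so some may enrol before a second AED is given. The ratio of 0.73 needs half of an assumed 40% seizure group on two AEDs at entry, all with abnormal MRI.
- Sampling error in the 18 infants is larger than a small shift. With log standard error √(0.52/(18 × 0.48)) = 0.245, the 95% range around a ratio of 1 is about 0.62 to 1.62.
- The planned MRI analysis is adjusted. Infants without seizures lose nobody to the exclusion, so adjustment removes part of the bias.
- A range of 0.7 to 1.1 already contains 1, so it can be met without any selection.
- Sections 8.1.6 and 9.2 already say that effectiveness is not powered, and the primary PK endpoint is unaffected.
- Baseline AED use may be recoverable from item 6 of Section 8.1.1 and from the eligibility check.

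All of this stands as a limit on size and certainty. It leaves the direction unchanged. Low power does not excuse a directional bias. A yes/no seizure covariate still pools hard-to-control and milder seizures in the comparator. It gives no protection to the NDI model or to the fixed 40% rule.

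**Conclusion.** The concern holds as a conditional one. The exclusion is explicit, it shares its threshold with the seizure outcome, and no matching restriction on the NICHD arm is planned. If that arm includes infants on more than one AED, the seizure, MRI and NDI comparisons shift towards safety and benefit.

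The crude MRI ratio would be about 0.95, 0.90 or 0.78 for an excluded share of 5%, 10% or 20% at 90% abnormal MRI. The bias in the adjusted MRI estimate would be smaller. It cannot be calculated, because MRI rates by seizure stratum are not given. The seizure figures rest on the further assumption that the 40% has this trial's definition, so they show sensitivity and are not expected rates.

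Two parts need no assumption about NICHD: the MRI seizure covariate is not limited to before dosing, and the NDI model names no covariates. The change is worth making because it is cheap and bears on the safety event that the protocol singles out.

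**What to change.** 1. In Section 9.4.3, replace the seizure covariate with seizures and AED count at or before enrolment, defined identically in both groups. Use it with encephalopathy severity for NDI as well as MRI. Record it explicitly at baseline in Section 8.1.1 and the Schedule of Activities.
2. Where infant-level NICHD data allow, restrict that arm to infants on at most one AED at entry. Otherwise label the MRI and NDI comparisons descriptive and show the risk ratio over an assumed excluded share of 5% to 20%.
3. In Sections 9.1 and 9.2, state that the 40% benchmark is not matched to this trial's entry exclusion or to its more-than-one-AED definition. Either use a benchmark with the same definition and entry restriction, or treat the seizure comparison as descriptive.

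The cost is analysis wording and one explicit baseline item; eligibility and treatment are unchanged. The downside is a smaller comparator and a less favourable, or descriptive-only, stated comparison.
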